**INTRODUCTION**

Acne vulgaris is a long term inflammatory disease of the pilosebaceous. It has high grade existence and is known to negatively influence quality of life [1]. It begins in adolescence with 30% to 100% popularity. Acne scarring is popular and well-recognized outcome of acne [2-3]. It may be either atrophic or hypertrophic, further categorized morphologically into boxcar, icepick or rolling with the option of treatment modalities often based on scar types [4]. Prior recognition and control of acne is necessary in averting scarring and resultant unfavorable social effects developed due to irritation and feeling of being ashamed [5]. Acne scars developed due to inadequate treatment or delayed healing of inflammatory acne lesions [6]. Gels of retinoids, like adapalene, raises collagen by stimulating fibroblast cells [7]. A home-based topical treatment is more accepted and would be suitable in treating scars [8].

Another research has shown the better results of tazarotene gel 0.1% with contrast to adapalene 0.1%, in controlling acne [9]. The aim of our study is comparison of daily use of tazarotene gel 0.1% in contrast to performing derma roller monthly sessions for controlling acne scars. Many previous studies reported, but there was lack of local researches in head to head

comparison between these two therapies, to improve outcome by adopting superior approach as first choice of treatment in future.

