Microneedling was conducted by dermaroller in constant rolling motion with slight pressure in variable paths (i.e, diagonal and right angled direction) with upward motion till pinpoint bleeding was seen. After session, the saline soaked gauze were put on that area. The patients were also directed for precise use of sunblock having sun protective factor 30 on full area of face. All patients were followed up at 3 month and then at 6 month from the initial visit. Data stored in the form of pictures. Excellent score was labelled to those patients who uplift by 2 grades, while good for 1 and poor for 0 grade. The results were noted from alterations of initial scar grade first at 3 then at 6 month appointment. All data was entered in a predesigned proforma.

Biasness and confounder were controlled by strictly following the inclusion criteria.

SPSS 21 analysed the data. Frequencies and percentages were enumerated for qualitative data like gender, scar type, treatment, scar severity grade at baseline, after 3 and 6 months and efficacy. Quantitative variables were presented as mean  $\pm$  SD like age and duration of acne. Comparison between both groups for efficacy was done by using Chi square test. Modifier like age, gender and time span of disease were organised through stratification. Post stratification, Chi square test was used for categorical variables. Consider  $P \leq 0.05$  as significant.

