### **STATISTICAL ANALYSIS**

In this randomized control trial, the total of 202 patients 101 in each group were included to compare the efficacy between topical tazarotene gel 0.1% versus Microneedling in treatment of atrophic post-acne scars and results were analyzed as:

Mean $\pm$ SD of age in group A (topical tazarotene gel 0.1%) was 26.3 $\pm$ 5.8 with C.I (25.15----27.44) and group B (Microneedling) was

25.2 $\pm$ 5.5 with C.I (24.11----26.28) years, as shown in **TABLE 1**.

Mean $\pm$ SD for duration of acne in group A (Topical tazarotene gel

0.1%) and group B (Microneedling) was 6.5 $\pm$ 3.1 and 6.1 $\pm$ 2.6 with C.I

(5.88----7.11) and (5.88----7.11) years, respectively as shown in **TABLE 2**.

In group wise distribution of gender, 36 (35.6%) male and 65 (64.4%) females were enrolled in group A (Topical tazarotene gel 0.1%) while 33 (32.7%) male and 68 (67.3%) females were included in group B (Microneedling) as shown in **TABLE 3**.

In distribution for type of scar icepick was noted in 36 (35.6%) patients, rolling 14 (13.8%), boxcar 12 (11.9%) and mixed 39 (38.7%) patients in group A (Topical tazarotene gel 0.1%) while in in group B (Microneedling) icepick was noted in 40 (39.7%), rolling 15 (14.6%), boxcar 20 (19.9%) and mixed 26 (25.8%) patients as shown in **TABLE 4**.

Baseline scar severity grades 1,2,3,4 was noted in 0 (0%), 0 (0%), 20 (19.8%), 81 (80.2%) and 0 (0%),0 (0%), 20 (19.8%), 81 (80.2%) in group A and group B respectively. While at 3 and 6 months it was noted as 03 (3%), 12 (11.9%), 26 (25.7%), 60 (59.4%), 22 (21.8%),

67 (66.3%) and 03 (3%), 23 (22.8%), 26 (25.7%), 49 (48.5%), 03 (3%), 14 (13.9%), 24 (23.8%), 50 (59.4%) in group A and group B respectively as shown in **TABLE 5**.

Excellent grade was noted in 12 (11.9%) and 10 (9.9%) patients in group A and group B, respectively. Good grade was noted in 25 (24.8%) and 21 (20.8%) in group A and group B while poor grades was documented in 64 (63.4%) and 70 (69.3%) patients in group A and group B, respectively as shown in **TABLE 6**.

Topical tazarotene gel 0.1% was found to be effective in 37 (36.6%) patients while microneedling, was found to be effective in 31 (30.7%) patients with non-significant P value i.e. (P=0.372) as shown in **TABLE 7**.

Stratification of age group (18---25) and >25 years, gender (male & female) and duration of acne (4----6) > 6years were done to assess the significant difference between both groups from (**TABLE 8-10**).

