**DISCUSSION**

Acne vulgaris is a frequent issue which might give scarring of different intensity and appearance which compromise the patients self-esteem and lead to insecurity, suspicion of inadequacy, social confinement, anxiety and depression [10]. So, it is necessary to control the scars. Acne scars divided into plain macules (erythematous or hyperpigmented), raised (keloids or hypertrophic scars) and reduced (icepick, boxcar, and rolling subtypes) [11]. Patients having scars gained from different treatment modalities corresponding to skin Fitzpatrick type, gender, age, health, mental and public component and scarring characteristics (type, site, and severity) [12,13]. Recent therapies include (chemical peeling, retinoid creams, corticosteroids, or 5-FU injectables), procedures (excision, subcision), non-invasive therapies (cryotherapy sessions and electro-surgery) and energy-based modalities (lasers, radiofrequency devices) [13]. Such modalities have different mode of actions, outcome and complications. The more intrusive therapies seldom demand trouble (e.g the necessity to keep away from sunlight), hyper - or hypopigmentation and lengthy recover time. Further new modality (e.g lasers) are generally costly, and the pharmacological modalities can lead to regional and extensive toxicities.

The US Food and Drug Administration accepted tazarotene, a topical third generation acetylenic retinoid, for acne control in June 1997 [14]. Tazarotene in the form of cream or lotion is equally beneficial [15-17]. It has also been shown to

remarkably control the macules of acne scarring in contrast to adapalene 0.3% gel [18].

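### The efficacy comparison is not adjusted for any baseline factor, and scar type, which the document itself treats as relevant, is only described

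*Combined protocol and SAP*

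**What the plan says.** The METHODOLOGY section compares efficacy between arms by chi-square. On baseline factors it says "Modifier like age, gender and time span of disease were organised through stratification", followed by chi-square tests after stratification. The STATISTICAL ANALYSIS section confirms which factors were used: "Stratification of age group (18---25) and >25 years, gender (male & female) and duration of acne (4----6) > 6years were done". Tables 8-10 give a p-value within each stratum and nothing that combines strata.

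Scar type has a descriptive role only: "Frequencies and percentages were enumerated for qualitative data like gender, scar type, treatment, scar severity grade at baseline". METHODOLOGY has it assessed by dermoscopy for every patient at the first visit.

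The document also says why scar type could matter. The INTRODUCTION describes scar morphology "with the option of treatment modalities often based on scar types". The DISCUSSION, listing what treatment benefit corresponds to, names age, gender and others together with "scarring characteristics (type, site, and severity".

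The reported distribution is "boxcar 12 (11.9%) and mixed 39 (38.7%) patients in group A", against "boxcar 20 (19.9%) and mixed 26 (25.8%) patients" in group B.

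**The concern.** Testing within strata does not adjust the comparison between arms. It splits the sample into smaller crude comparisons and leaves the overall estimate as it was. The reported difference is therefore unadjusted for age, gender and duration as well as for scar type.

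Scar type is the clearest gap because it has not even been examined within strata. The document takes age and gender from its own list of factors bearing on benefit and leaves scar type aside. If scar types respond differently, part of the observed difference may reflect scar mix, or a difference may be partly hidden by it. The report also cannot say how either treatment performs by scar type, although it says treatment is often chosen on that basis.

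**Working it through.** **Inputs.** Efficacy: 37/101 (A) and 31/101 (B), Table 7. Scar type, Table 4 counts: A icepick 36, rolling 14, boxcar 12, mixed 39; B 40, 15, 20, 26. Strata: Tables 8-10. Percentages below are recomputed from counts, so some differ from the printed ones in the last digit.

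**1. The document's own figure.** Chi-square = 202 × (37×70 − 64×31)² / (101×101×68×134) = 0.798, 1 df, p=0.372. This reproduces Table 7. The six stratum p-values (0.739, 0.245, 0.738, 0.359, 0.725, 0.187) also reproduce.

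**2. Precision of the crude result.** Difference = 36.6% − 30.7% = 5.9 points. SE = √[(37×64 + 31×70)/101³] = 6.6 points. 95% CI: -7.1 to 18.9 points.

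**3. Scar type by arm.** With equal arms, chi-square = Σ(a−b)²/(a+b):

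| Type | A | B | Gap, points | (a−b)²/(a+b) |
|---|---|---|---|---|
| Icepick | 36 | 40 | -4.0 | 16/76 = 0.21 |
| Rolling | 14 | 15 | -1.0 | 1/29 = 0.03 |
| Boxcar | 12 | 20 | -7.9 | 64/32 = 2.00 |
| Mixed | 39 | 26 | +12.9 | 169/65 = 2.60 |

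The total is 4.85 on 3 df, p=0.18. Mixed against the rest gives 3.83 on 1 df, p=0.050, but that contrast picks out the largest gap after seeing the table. The standardised difference is 0.28 for mixed and 0.31 over all four types.

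**4. The other factors.** Aged 18-25: 41 vs 56 (14.9 points, p=0.035). Duration 4-6 years: 53 vs 62 (8.9 points, p=0.20). Male: 36 vs 33 (3.0 points, p=0.66). Only age has a larger gap than mixed scars.

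**5. What adjustment does where the tables allow it.** The Mantel-Haenszel risk difference weights each stratum by n_A×n_B/N.

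- Duration, 4-6 years: 13/53 − 17/62 = -2.9 points, weight 53×62/115 = 28.6.
- Duration, over 6 years: 24/48 − 14/39 = +14.1 points, weight 48×39/87 = 21.5.
- Pooled: (28.6×(-2.9) + 21.5×14.1)/50.1 = 4.4 points, against 5.9 crude.

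Mantel-Haenszel odds ratios are 1.23 for duration (p=0.50), 1.38 for age (p=0.29) and 1.33 for gender (p=0.34), against 1.31 crude. The estimate moves a little, in both directions.

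**6. Scar type.** Efficacy by scar type is not reported, so the adjusted value cannot be computed. Mixed is the only type more common in A, and the other three gaps sum to -12.9. If mixed scars differ from the rest by a fixed gap g in both arms, the crude difference shifts by 0.129 × g:

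| Assumed g, points | Shift, points (either direction) |
|---|---|
| 10 | 1.3 |
| 20 | 2.6 |
| 30 | 3.9 |
| 40 | 5.1 |

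For scale, response in this trial differs by 17.6 points across duration: 30/115 = 26.1% against 38/87 = 43.7%. Removing the whole 5.9 points would need g of about 5.94/0.1287 = 46 points.

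**7. Could significance change?** Take g = 40 in the direction that enlarges the difference: 5.94 + 5.15 = 11.1 points. With the crude SE of 6.6, z is about 1.67 and p about 0.10. A covariate that strong would also reduce the SE. Mixed would respond at 6.5% and the rest at 46.5% (68/202 = 33.7% overall; 65/202 = 32.2% mixed). The mean within-type variance is then 0.322×0.065×0.935 + 0.678×0.465×0.535 = 0.188, and SE = √(2×0.188/101) = 6.1 points, so p is about 0.07. It stays above 0.05.

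**The case against.** The strongest reply is that allocation was random, so no adjustment is needed for validity, and a four-category p of 0.18 is unremarkable. That stands. A reader might infer from the mixed-scar gap that the randomisation failed; the figures do not support this. The reason to include scar type is its possible prognostic value, and the documents assert that value in general terms without quantifying it for these two treatments.

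A reader might also infer that the comparison is unadjusted because scar type is missing from the list of modifiers. It is not: adding it there would only produce another set of within-stratum tests. The list is worded openly, but the tables show that three factors were used, and none of the three is adjusted for.

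The response gaps of 10 to 40 points have no source in the documents, and 40 is extreme. That also stands, and is why a range is shown.

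Finally, adjustment has costs. Rolling (14 and 15 patients) and boxcar (12 and 20) are sparse, an interaction test would have little power, and choosing covariates after the results are known adds flexibility. These points limit how results by type may be read. They do not remove the case for one adjusted estimate from data already collected.

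**Conclusion.** The point holds. No adjusted efficacy estimate exists for any baseline factor, and scar type is not used beyond description although it was recorded for every patient and the document calls it relevant.

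The size of the effect is unknown. Under the assumed gaps, scar mix would shift the 5.9-point difference by 1.3 to 5.1 points in either direction. This rests on a gap that is equal in both arms and on the other three types sharing one response rate.

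A reader might go further and say that adjustment would overturn the non-significant result. Nothing in the documents supports that, and no assumed gap up to 40 points does so. What is affected is the conclusion that the treatments are comparable. The interval of -7.1 to 18.9 points is itself the larger obstacle to that conclusion; a shift of a few points adds to it.

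**What to change.** Add one adjusted efficacy analysis and report the adjusted A-B difference with its 95% CI beside the crude one. Label it post hoc, since results are known.

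- **Model.** Use logistic regression with arm, scar type, age, gender, duration and baseline grade, and convert the result to a risk difference by averaging predictions over all patients. Grade is there for precision only, as it is identical between arms (20 at grade 3 and 81 at grade 4 in each). A Mantel-Haenszel estimate is a simpler alternative for scar type alone. Stratifying on all five factors at once would give 4×2×2×2×2 = 64 cells for 202 patients.
- **By scar type.** Show efficacy by arm within each type with 95% CIs, and one arm-by-scar-type interaction test, all marked exploratory.
- **Definition.** Define the mixed category. It has the largest gap between arms but is not among the example types given for the dermoscopic assessment in METHODOLOGY.

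**Cost.** No new data, but a new model. With age and duration as single linear terms it has 1+3+1+1+1+1 = 8 parameters besides the intercept for 68 responders, about 8.5 per parameter, which is workable but not generous. Intervals for rolling and boxcar scars will be wide.

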### **STATISTICAL ANALYSIS**

In this randomized control trial, the total of 202 patients 101 in each group were included to compare the efficacy between topical tazarotene gel 0.1% versus Microneedling in treatment of atrophic post-acne scars and results were analyzed as:

Mean $\pm$ SD of age in group A (topical tazarotene gel 0.1%) was 26.3 $\pm$ 5.8 with C.I (25.15----27.44) and group B (Microneedling) was

25.2 $\pm$ 5.5 with C.I (24.11----26.28) years, as shown in **TABLE 1**.

Mean $\pm$ SD for duration of acne in group A (Topical tazarotene gel

0.1%) and group B (Microneedling) was 6.5 $\pm$ 3.1 and 6.1 $\pm$ 2.6 with C.I

(5.88----7.11) and (5.88----7.11) years, respectively as shown in **TABLE 2**.

In group wise distribution of gender, 36 (35.6%) male and 65 (64.4%) females were enrolled in group A (Topical tazarotene gel 0.1%) while 33 (32.7%) male and 68 (67.3%) females were included in group B (Microneedling) as shown in **TABLE 3**.

In distribution for type of scar icepick was noted in 36 (35.6%) patients, rolling 14 (13.8%), boxcar 12 (11.9%) and mixed 39 (38.7%) patients in group A (Topical tazarotene gel 0.1%) while in in group B (Microneedling) icepick was noted in 40 (39.7%), rolling 15 (14.6%), boxcar 20 (19.9%) and mixed 26 (25.8%) patients as shown in **TABLE 4**.

Baseline scar severity grades 1,2,3,4 was noted in 0 (0%), 0 (0%), 20 (19.8%), 81 (80.2%) and 0 (0%),0 (0%), 20 (19.8%), 81 (80.2%) in group A and group B respectively. While at 3 and 6 months it was noted as 03 (3%), 12 (11.9%), 26 (25.7%), 60 (59.4%), 22 (21.8%),

67 (66.3%) and 03 (3%), 23 (22.8%), 26 (25.7%), 49 (48.5%), 03 (3%), 14 (13.9%), 24 (23.8%), 50 (59.4%) in group A and group B respectively as shown in **TABLE 5**.

Excellent grade was noted in 12 (11.9%) and 10 (9.9%) patients in group A and group B, respectively. Good grade was noted in 25 (24.8%) and 21 (20.8%) in group A and group B while poor grades was documented in 64 (63.4%) and 70 (69.3%) patients in group A and group B, respectively as shown in **TABLE 6**.

Topical tazarotene gel 0.1% was found to be effective in 37 (36.6%) patients while microneedling, was found to be effective in 31 (30.7%) patients with non-significant P value i.e. (P=0.372) as shown in **TABLE 7**.

Stratification of age group (18---25) and >25 years, gender (male & female) and duration of acne (4----6) > 6years were done to assess the significant difference between both groups from (**TABLE 8-10**).

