## **CONCLUSION**

It is to be concluded that efficacy of daily home based tazarotene gel application was comparable with monthly sessions of microneedling therapy in treating atrophic post-acne scars.

**CONFLICT OF INTEREST:** None.

**ETHICAL APPROVAL:** Ethical approval was taken from Institutional Review Board Jinnah Postgraduate Medical Center Hospital, Karachi prior to the initiation of the study.

**PATIENT'S CONSENT:** Informed consents were obtained from patients to publish the data concerning this case.

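### Group A's outcome split (12 Excellent, 25 Good, 64 Poor) cannot arise from its own 6-month grades in Table 5, so the count behind the only efficacy comparison is unverified

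*Combined protocol and SAP*

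**What the plan says.** The Methodology defines the outcome by grade change from the initial visit: "Excellent score was labelled to those patients who uplift by 2 grades, while good for 1 and poor for 0 grade". Grades were recorded at 3 and at 6 months.

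Table 5 gives the grades. At baseline each group has 20 patients at grade 3 and 81 at grade 4. For Group A at 6 months, the Statistical Analysis text lists grades 1 to 4 as "03 (3%), 23 (22.8%), 26 (25.7%), 49 (48.5" (the quotation stops inside the last percentage), in agreement with Table 5.

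For Table 6 the same section states "Excellent grade was noted in 12 (11.9%) and 10 (9.9%) patients in group A and group B, respectively". The Good counts are 25 for Group A against 21 for Group B, and the Poor counts are 64 against 70.

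For Table 7, "Topical tazarotene gel 0.1% was found to be effective in 37 (36.6%) patients", against 31 for microneedling, with p = 0.372. The Conclusion is that "efficacy of daily home based tazarotene gel application was comparable with monthly sessions of microneedling therapy". Tables 6 and 7 carry no timepoint.

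**The concern.** Table 6 should be a recoding of the grade changes whose margins Table 5 shows. Margins do not fix every patient's change, but they limit which splits are possible, and Group A's split lies outside those limits. At least one printed Group A figure must then be wrong if the outcome was taken at 6 months.

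Effective yes/no is the trial's only between-group efficacy result, and it comes from these same grade changes. The chi-square test uses 37 v 64, not the Excellent/Good division, so it survives if 37 is right. Some ways of removing the contradiction leave p unchanged. Others make the difference significant in favour of tazarotene.

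**Working it through.** **Reported test.** Uncorrected chi-square on 37/64 v 31/70:

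202 × (37×70 − 64×31)² / (101 × 101 × 68 × 134) = 202 × 606² / 92,951,512 = 0.798, p = 0.372. The printed value is correct for these counts.

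**Grade totals, Group A.**
- Baseline: 20×3 + 81×4 = 384.
- 6 months (3/23/26/49): 3×1 + 23×2 + 26×3 + 49×4 = 323.
- Net fall: 384 − 323 = 61 grades.
- Table 6: 12×2 + 25×1 = 49 grades. Only three patients end at grade 1, so at most three can have gained 3 grades. Counting those as Excellent gives at most 49 + 3 = 52.

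The shortfall is at least 9 grades. Any worsening would require more than 61 grades of improvement and so widens the gap.

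**All possible transitions, Group A.** Let a, b and w be the numbers moving from grade 3 to grades 1, 2 and 4, with a ≤ 3 and a + b + w ≤ 20. The margins then fix the rest: 4→1 is 3 − a, 4→2 is 23 − b, 4→3 is 6 + a + b + w, and 4→4 is 49 − w. Counting 2 or more grades as Excellent and no change or worse as Poor:
- Excellent = 26 − b
- Good = 6 + a + 2b + w
- Effective (Excellent + Good) = 32 + a + b + w, so 32 to 52

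Twelve Excellent forces b = 14, and then Good = 34 + a + w, which is at least 34 and cannot be 25. No transition table gives 12/25/64, with or without worsening.

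**What each reconciliation implies** (Group B held at 31/101, uncorrected chi-square):

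| Taken as right | Effective in A, no worsening | p | With worsening |
|---|---|---|---|
| Table 5 only | 32 to 52 | 0.88 to 0.003 | same range |
| Table 5 and 37 effective | 37 (Excellent 21 to 24) | 0.372 | Excellent up to 26 |
| Table 5 and 25 Good | 42 to 43 | 0.107 to 0.080 | up to 51, p = 0.004 |
| Table 5 and 12 Excellent | 46 to 49 | 0.030 to 0.010 | up to 52, p = 0.003 |
| Table 6, with Table 5 wrong | 37 | 0.372 | same |

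The plan's threshold of p ≤ 0.05 is crossed between 44 (p = 0.058) and 45 (p = 0.042).

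**Group B as a control.** Its 6-month grades are 3/14/24/60. Table 5 prints 60 at grade 4; the text prints 50, but then the four counts sum to 91, and 59.4% of 101 is 60. The total falls from 384 to 3 + 28 + 72 + 240 = 343, a drop of 41, and 2×10 + 21 = 41. Exactly one pattern without worsening gives 10/21/70: grade 3 to 1/2/3 is 3/7/10, and grade 4 to 2/3/4 is 7/14/60. The definition and the 6-month timepoint therefore work for Group B.

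**3-month grades instead.** Group A is 3/12/26/60 and Group B is 3/9/22/67. Without worsening these allow at most 36 effective in A and 26 in B, below the reported 37 and 31. By the same algebra, 12/25/64 needs a + w = 13 with a ≤ 3, so at least 10 grade-3 patients in A worsened; 10/21/70 needs a + w = 15, so at least 12 in B worsened, out of 20 in each group. Six months is the likely timepoint, but it is not stated.

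**Stratified tables.** Tables 8 to 10 return the same totals: A is 16+21, 10+27 and 13+24, each 37; B is 20+11, 8+23 and 17+14, each 31.

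**The case against.** The strongest reply concerns weight, not arithmetic. The count of 37 appears in Table 7, in all three stratified tables, in the summary and in the Discussion. For the result to become significant, Group A needs 45 or more effective patients, so all of those would have to be wrong together. The scenario with 46 or more keeps one Group A cell of Table 6 and rejects the other two. The simpler explanations are an error in Group A's column of Table 5 or in the division of 37 into 12 and 25; both leave p at 0.372. The split itself is never tested.

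Much of this stands. An error in the tested count is not shown, and the significant scenarios are conditional and fit Tables 7 to 10 less well. But those tables presumably share one coded variable, so their agreement shows that 37 was used consistently, not that it was derived correctly from the grades.

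Three narrower points also stand as limits. That effective means Excellent plus Good is inferred from 12 + 25 = 37 and 10 + 21 = 31; the documents never say so. Group B is held at 31 because its split fits, although its 6-month margins alone would allow 21 to 38 (up to 41 with worsening). The switch at 45 depends on the uncorrected test, which is the one that reproduces 0.372; with continuity correction 45 gives p = 0.059 and 46 gives p = 0.043.

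**Conclusion.** The contradiction is certain on the 6-month reading: Group A's three outcome counts and its Table 5 grades cannot all be right. The 3-month reading escapes it only if at least half of Group A's grade-3 patients, and at least 12 of 20 in Group B, got worse, and the outcome definition has no category for worsening. The Group A figures agree between text and tables, and their percentages match their counts, so this is not a reading error in one place.

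What follows for the result is open. If 37 is right, p stays at 0.372 and only a descriptive table needs correcting. If the 6-month grades and the 12 Excellent are both right, every possible table has at least 46 effective patients in Group A (45.5% v 30.7%, p = 0.030 or smaller), and the stated conclusion would not hold. The documents cannot settle which. Because this is the only efficacy comparison, it must be resolved before the conclusion is relied on. The ranges assume that effective means Excellent plus Good, that a 3-grade gain counts as Excellent and worsening as Poor, and that Group B has 31 effective.

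**What to change.** 1. From the proformas, rebuild the cross-tabulation of baseline grade by 6-month grade for each arm.
2. Derive Excellent, Good, Poor and effective yes/no from it by program. State that effective is Excellent plus Good, if that is the rule, and how a 3-grade gain and a worsening are counted.
3. Correct whichever of Tables 5 to 7 is wrong, correct the 50 printed in the text for Group B at grade 4, and give Tables 6 and 7 a timepoint.
4. If the effective counts change, rerun the chi-square test and Tables 8 to 10 and reword the conclusion to match. If they do not, correct only the wrong table and leave p = 0.372.

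The cost is a few hours of data checking on records already collected, with no new patients.
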